# **1. STUDY IDENTIFICATION**

Unique Protocol Identification Number: NCT03493035 Brief Title: Risk Factors of Middle Cerebral Artery Aneurysm (MCAA) Official Title: A Case-Control Study of Independent Predictors of Middle Cerebral Artery Aneurysm Study Type: Observational

# 2. STUDY STATUS

Entered Document Date: July 12, 2017 Record Verification Date: February 14, 2019 Overall Recruitment Status: Completed Study Start Date: June 2015 Study Completion Date: June 2017

## 3. SPONSORS/COLLABORATORS

Responsible Party, by Official Title: Principal Investigator

# 4. OVERSIGHT

**Human Subjects Review:** The protocol of the study was approved by the Institutional Review Board, and written informed consent will be sought from all the study participants. **Human Subjects Protection Review Board Status:** Submitted, approved

## **5. STUDY DESCRIPTION**

## **Brief Summary:**

Current evidence suggests that a principal factor involved in formation, enlargement and rupture of cerebral aneurysms are hemodynamic forces acting at arterial bifurcation [1]. Both experimental studies in dogs and computational fluid dynamics (CFD) studies demonstrated that high levels of wall shear stress (WSS) at arterial bifurcation and high positive WSS gradient (WSSG) may lead to remodelling of vascular epithelium and destruction of internal elastic membrane, and thus, may play a role in aneurysm formation [2]. While the contribution of WSS to aneurysm development raises no controversies, the question whether

arterial bifurcation morphology might influence the shear stress level is still a matter of discussion. The results of glass model studies conducted in the 1970s and more recent CFD simulations imply that the magnitude of hemodynamic stress and its distribution at arterial bifurcation depend on blood flow characteristics and the bifurcation's geometry [3-7].

MCA is one of three sites predisposed to aneurysm formation [8]. Unlike other two predilected locations, anterior communicating artery complex (ACoA) and internal carotid artery (ICA), MCA is not strictly a part of the arterial circle of Willis. The use of the MCA model will enable to minimize the influence of collateral blood flow through communicating arteries in asymmetrical forms of the circle of Willis on hemodynamic parameters, and the effect of circle geometry on the size of bifurcation angles.

#### **Objectives of Study:**

i) to determine morphometric and hemodynamic parameters of aneurysmal and nonaneurysmal MCA bifurcations and ii) to analyse their relationship with aneurysm formation.

## 6. CONDITIONS AND KEYWORDS

## Primary Disease or Condition Being Studied in the Trial, or the Focus of the Study:

1. Patients (further referred to as cases) diagnosed with unruptured MCA aneurysm.

2. Patients (further referred to as controls) with no evidence of intracranial pathologies on 3D

CTA, directed at CT examination due to minor symptoms, such as headache or vertigo.

#### 7. STUDY DESIGN (OBSERVATIONAL)

**Observational Study Model:** Case-Control

Time Perspective: Prospective

Enrollment Type: Actual

Number of Groups/Cohorts: 2; Case/Control

Patient Registry Information: All patients were admitted to the unit based on their signed consent form

**Target Follow-Up Duration: NA** 

#### **Study Design:**

## 3D CTA Protocol:

All studies will be performed with a 64-row 128-slice CT system (GE Optima CT 660, GE Healthcare, USA) using the following parameters: collimation 39.38 x 0.625 mm, spiral pitch

0.516:1, anode voltage 120 kV, anode amperage 40-500 mA, rotation time 0.6 seconds, slice thickness 0.625 mm. Patients will receive intravenous non-ionic contrast agent (Iomeron 350, Bracco Imaging Deutschland GmbH, Konstanz, Germany) at volume adjusted to their body weight, up to 50 mL, followed by a 30 mL NaCl flush. Iomeron 350 will be given to the basilic vein at a rate of 4-4.5 mL/second with the aid of an automatic syringe (OptiVantage DH, Mallincrodt, St Louis, MO, USA). The scanning will begin 15-20 seconds after administration of the contrast agent, after reaching attenuation of 100-HU above the baseline attenuation, and will last for 6 seconds. The images will be recorded as digital imaging and communications in medicine (DICOM) files on a HP Z800 workstation.

#### Morphometric Analysis of MCA Bifurcations:

3D CTA scans data in DICOM format will be transferred to Mimics Innovation Suite (MIS) platform (Materialise, Leuven, Belgium). Image segmentation and creation of 3D models will be carried out with Mimics v.17.0 MIS software (Materialise, Leuven, Belgium). The process of segmentation will include main trunks of the MCA and the post-bifurcation branches. Trifurcations of the main MCA trunk will be excluded from the morphometric analysis. MCA bifurcations from the aneurysm patients will be divided into two groups: the An group with aneurysmal MCA bifurcations and the non-An group with contralateral non-aneurysmal MCA bifurcations. Also, MCA bifurcations from the controls will be divided into two groups: R-MCA group with bifurcations of the right MCA and the L-MCA group with bifurcations of the left MCA. Before the morphometric calculations, the MCA aneurysms in the An group will be digitally erased using the Mimics software. After completing the 3D model, the vessel centreline will be fitted automatically with a computer-aided design (CAD) tool. The other parameters: tortuosity, the largest curvature of MCA main trunk and the largest curvatures of the two post-bifurcations branches will be calculated automatically according to the centreline. The points of the largest curvature will be set as close to the bifurcation as possible, but in a distance longer than 5 mm. Based on these points, the cross-sectional area and the best fit diameter of the MCA trunk (p0 and d0, respectively) and its two postbifurcation branches (p1, d1 and p2, d2 for the larger and smaller branch, respectively) will be estimated. The best fit diameters will be then used to calculate the radii of the main MCA trunk  $(r_0)$  and its branches  $(r_1 \text{ and } r_2 \text{ for the larger and smaller branch, respectively})$  using the following formula:

$$r=d/2$$
 (1)

where r - radius and d - the best fit diameter. The radii will be used to calculate two ratios describing the bifurcation asymmetry:

asymmetry ratio=
$$r_2^2 r_1^{-2}$$
 (2)

and

area ratio=
$$(r_1^2 + r_2^2)r_0^{-2}$$
 (3)

The centrelines and the largest curvature points will be exported to 3-matic v.9.0 MIS software to determine angles between the bifurcation components. The apices of the angles will be defined as the largest curvature points for the MCA trunk and its both branches, and the intersection of both centrelines. The angle between the post-bifurcation branches ( $\alpha$  angle) will be calculated, along with the angles between the MCA trunk and the larger and the smaller branch ( $\beta$  and  $\gamma$  angle, respectively). Finally, the angles between each post-bifurcation branch and the direction of the MCA trunk will be calculated as:

$$\Phi_1 = 180 - \beta$$
 (4)

$$\Phi_2 = 180 - \gamma \tag{5}$$

Transcranial Color-Coded Sonography (TCCS) Protocol:

All TCCS examinations will be performed by the same researcher using a Vivid 3 Pro (GE Healthcare, Chicago, Illinois, USA) equipped with a multi-frequency transcranial probe (1.5-3.6 MHz), according to the previously described standards [9]. Anterior cerebral circulation will be imaged through the temporal acoustic window with the subject in a supine position. Angle-corrected mean blood flow velocity ( $V_m$ ), peak systolic velocity ( $V_{ps}$ ) and end-diastolic velocity ( $V_{ed}$ ) will be measured for both MCAs. Pulsatility index (PI) and volume flow rate (VFR) in each vessel will be calculated as:

$$PI=(V_{ps}-V_{ed})V_{m}^{-1}$$
(6)

$$VFR = V_m p_0 \tag{7}$$

where  $p_0 - a$  cross-sectional area of the main MCA trunk.

#### Analysis Plan:

The following variables will be evaluated as potential risk factors for MCA aneurysm formation: radii and cross-sectional area of the main MCA trunk ( $r_0$ ,  $p_0$ ) and its branches ( $r_1$ ,  $p_1$  and  $r_2$ ,  $p_2$  for the larger and smaller branch, respectively), tortuosity of MCA trunk, asymmetry ratio,  $r_2^2 r_1^{-2}$ , area ratio,  $(r_1^2+r_2^2)r_0^{-2}$ ,  $\Phi_1$  (°),  $\Phi_2$  (°),  $\alpha$  (°),  $V_m$  (cm/s), VFR (cm^3/s) and PI. Normal distribution of the study variables will be verified with Shapiro-Wilk test. The significance of intergroup and intragroup differences will be verified with Mann-Whitney U-

test and Wilcoxon signed-rank test, respectively. All morphological and hemodynamic parameters shown to differ significantly between the study groups will be subjected to logistic regression analysis with stepwise addition mode. The potential predictors of MCA aneurysm will be identified on univariate analysis, and the relationship between pairs of the significant predictors will be determined based on Pearson's linear correlation coefficients. The variables with *P*-values <0.1 on univariate analysis, except those being correlated with one another, will be included in multivariate logistic regression model, to identify independent predictors of MCA aneurysm. The results will be presented as odds ratios (ORs) and their 95% confidence intervals (CIs). The independent predictors of MCA aneurysm will be subjected to receiver operating characteristic (ROC) analysis to identify their cut-off values with optimal sensitivity and specificity. The results will be considered statistically significant for p-values <0.05. Statistical analyses will be performed with Statistica v.13.3 package (StatSoft, Tulsa, Oklahoma, USA).

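### The Analysis Plan describes entry to the logistic model twice and never reconciles the two, so the reported independent predictors depend on which sentence is followed

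*Combined protocol and SAP*

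**What the plan says.** Everything relevant is in the Analysis Plan (section 7), which gives two routes into the logistic model.

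- **Route A.** "All morphological and hemodynamic parameters shown to differ significantly between the study groups will be subjected to logistic regression analysis with stepwise addition mode". The level comes from a later sentence: "The results will be considered statistically significant for p-values <0.05". The tests are named just before: "The significance of intergroup and intragroup differences will be verified with Mann-Whitney" for comparisons between groups, and Wilcoxon signed-rank for those within groups.
- **Route B.** "The potential predictors of MCA aneurysm will be identified on univariate analysis". Next, "the relationship between pairs of the significant predictors will be determined based on Pearson's linear correlation coefficients". Finally, variables with P "<0.1 on univariate analysis, except those being correlated with one another, will be included in multivariate logistic regression model".

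The list introduced by "The following variables will be evaluated as potential risk factors for MCA aneurysm formation" has 15 entries: three radii, three cross-sectional areas, tortuosity, two ratios, three angles, mean velocity, volume flow rate and pulsatility index. Variables that survive as independent predictors go on to ROC analysis for cut-offs.

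The plan leaves five things open:

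- whether the univariate step starts from all 15 candidates or only from those that passed Route A;
- which group comparison counts for Route A;
- whether the multivariable model is itself stepwise;
- the P-values for stepwise entry and removal;
- the size of correlation that excludes a variable, and which of a pair is kept.

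**The concern.** A 0.1 screening level is normally chosen so that borderline variables are still available for joint modelling. Route A already removes variables that do not reach 0.05, so if it comes first it defeats that purpose. If Route A is instead a separate way of building the model, two analysts can each follow the text faithfully and fit different models to the same data. One lets an entry test choose among variables significant at 0.05. The other takes uncorrelated variables with P<0.1 into one model.

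The official title (section 1) names independent predictors as the subject of the study. The open choice therefore reaches its main result: which variables are named, their adjusted odds ratios and intervals, and the cut-offs derived from them.

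**Working it through.** The plan has no figure of its own to reproduce here. The minimum of 75 cases and 75 controls (section 9) carries no effect size or power.

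**Inputs from the document:** 75 per group, 15 candidates, levels 0.05 and 0.1. **Assumed:** two-sided tests, effect sizes, distributions, correlations between candidates, and a stepwise entry level of P<0.05.

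**1. Sequential reading, closed form.** Take a shift of d = 0.3 SD.

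- Univariate screen at 0.10: noncentrality 0.3 × √(75/2) = 1.837; power ≈ Φ(1.837 − 1.645) = Φ(0.192) = 0.576.
- Mann-Whitney at 0.05, efficiency 0.955: noncentrality 0.3 × √(37.5 × 0.955) = 1.795; power ≈ Φ(1.795 − 1.960) = Φ(−0.165) = 0.435.
- If nearly every variable that passes at 0.05 also has P<0.1, the share lost is 1 − 0.435/0.576 = 0.245.

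**2. Sequential reading, simulation.** 4,000 runs per row, Mann-Whitney p<0.05 against univariate logistic P<0.1. For skewed data the shift is on the log scale (log-SD 0.5).

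| Data | Shift (SD) | Pass 0.05 filter | P<0.1 | Of those passing the filter, also P<0.1 | Of those with P<0.1, lost to the filter |
|---|---|---|---|---|---|
| Normal | 0 | 5.3% | 10.4% | 98.6% | 49.5% |
| Normal | 0.2 | 23.0% | 34.3% | 98.7% | 33.8% |
| Normal | 0.3 | 42.8% | 56.7% | 99.5% | 24.8% |
| Normal | 0.5 | 82.9% | 90.9% | 99.97% | 8.9% |
| Skewed | 0 | 5.0% | 9.7% | 84.5% | 56.4% |
| Skewed | 0.3 | 42.4% | 51.7% | 92.3% | 24.4% |
| Skewed | 0.5 | 85.2% | 89.0% | 97.7% | 6.4% |

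The 0.1 screen removes almost nothing that the filter has passed. The filter removes about a quarter of what P<0.1 would admit at 0.3 SD and 6% to 9% at 0.5 SD. The losses at zero shift are false leads, not a harm.

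**3. Same reading, paired filter.** In the Morphometric Analysis section, "MCA bifurcations from the aneurysm patients will be divided into two groups", aneurysmal and contralateral. If a Wilcoxon difference between those two sides also counts for Route A, and cases and controls do not truly differ, only about 9% to 10% of the variables passing the filter reach P<0.1. The 0.1 screen then does real work.

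**4. Alternatives reading.** 15 candidates, 3 or 6 with a true shift of 0.3 or 0.5 SD, common correlation 0, 0.2 or 0.3, 600 runs per setting. Route A is the filter plus forward stepwise entry; Route B enters all variables with P<0.1 together. A variable counts as independent if its final P<0.05.

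- Route B admits about 0.8 to 1.3 more candidates.
- Candidate sets differ in 55% to 77% of studies.
- Final sets differ in 28% to 74%. A second set of runs (correlation 0 or 0.3, effects 0.3 to 0.5) gave 28% to 80%.
- With identical P<0.1 candidates, stepwise against joint entry alone changes the final set in 15% to 68%.

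The correlation exclusion was not simulated because the plan gives no cut-off.

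**5. Interval coverage.** In that second set, 95% intervals after filter plus stepwise covered 62% to 89% of the time, against 79% to 97% with joint entry. A repeat on similar assumptions gave the same direction when every variable in the model was counted and each model was compared with its own adjusted odds ratios. When only variables with final P<0.05 were counted, joint entry had no consistent advantage.

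**The case against.** The strongest reply is that nothing here is a proven contradiction. The sentences can be read as one chain: group difference, univariate screen, correlation filter, stepwise fit. Saying that variables are included in a model does not say that they enter together, so stepwise addition may simply be the fitting method for that model. This stands as a possible reading.

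Three stronger claims might be inferred, and the document does not support them.

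- **That the rules conflict and the 0.1 rule is also inert.** These belong to different readings. In sequence the rules are compatible and 0.1 is redundant; as alternatives they diverge and 0.1 is fully active.
- **That 0.1 is inert in any case.** This needs a case-control Mann-Whitney filter, which the plan does not specify. With skewed data the 0.1 screen still removes up to about 15% of the variables that passed.
- **That every variable with P<0.1 goes in.** The plan exempts mutually correlated ones. This matters because volume flow rate is built from mean velocity and trunk area, both ratios come from the radii, and each area shares its cross-section with a radius.

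It is also fair to say that the percentages rest on assumed effects, and that univariate screening followed by joint entry is itself data-driven. But the chain reading does not rescue the plan. It discards borderline variables before adjustment and leaves stepwise selection, with its poor coverage, as the last step.

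**Conclusion.** The point holds as a failure to reconcile two entry rules, and it should be fixed because the headline result depends on it. Either main reading has a cost. In sequence, with a case-control Mann-Whitney filter, the stated 0.1 threshold is nearly redundant and about a quarter of the variables it would admit are lost at a 0.3 SD shift. As alternatives, the final predictors differ in roughly 28% to 80% of simulated studies. Filter plus stepwise entry also yields 95% intervals that are too narrow for what has been selected (coverage 62% to 89%, against 79% to 97%).

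The text alone establishes the ambiguity. The sizes depend on the assumed effects, correlations and 0.05 entry level, and the coverage gain applies to reporting all entered variables. Section 2 records the study as completed in June 2017. A reader might infer that the rule was picked after seeing results; the document does not show that, only that the text leaves room for it.

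**What to change.** Keep Mann-Whitney and Wilcoxon as descriptive comparisons, and delete the sentence that makes a significant difference the condition for stepwise logistic regression. Replace both routes with one rule:

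1. Start from all 15 listed candidates.
2. Screen each by univariate logistic regression on aneurysm status at P<0.1.
3. Apply the correlation exclusion with a stated |r| cut-off and a rule, fixed in advance, for which variable of a pair is kept.
4. Enter the remaining variables together, without stepwise addition, and report the odds ratio and interval for every variable entered, not only those with p<0.05.

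A model prespecified on subject-matter grounds would also remove the problem.

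Because the study is recorded as completed, this is not only a wording change. The report should disclose which rule was used and give the result under the other as a sensitivity analysis.

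The cost is a short text change, one further model fit, a slightly larger model with wider intervals and, where candidates are correlated, fewer variables reaching p<0.05.

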# 9. ELIGIBILITY

Sex/Gender: male and female, a minimum of 75 cases and 75 age- and sex-matched controls Age Limits: <75 years

**Eligibility Criteria:** The study will include patients (further referred to as cases) with unruptured MCA aneurysm diagnosed on three-dimensional computed tomography angiography (3D CTA).

Case inclusion criteria

- all patients with unruptured MCA aged between 18-75 years

Case exclusion criteria

- refusal to participate in the study
- inability to give informed consent
- presence of multiple cerebral aneurysms

- presence of pathologies, other than MCA aneurysm, in the central nervous system that could have a potential effect on cerebral blood flow (e.g. ischemic stroke, intracerebral or subarachnoid haemorrhage)
- severe systemic disorders (e.g. neoplastic disease)
- severe heart failure or multi-organ failure
- hemodynamically significant internal carotid artery stenosis
- pregnancy
- family history of cerebral aneurysms.

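### Fifteen candidates are tested without multiplicity control and filtered on the outcome, so the predictor claims, and the ORs and 95% CIs of null or weak predictors, lack their nominal error properties

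*Combined protocol and SAP*

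**What the plan says.** The Analysis Plan (section 7) introduces its candidates with "The following variables will be evaluated as potential risk factors for MCA aneurysm formation" and lists 15: r0, p0, r1, p1, r2, p2, trunk tortuosity, asymmetry ratio, area ratio, Φ1, Φ2, α, Vm, VFR and PI. The filters are:

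- a group-comparison screen: "The significance of intergroup and intragroup differences will be verified with Mann-Whitney U" (with the signed-rank test for the intragroup part);
- stepwise selection: "All morphological and hemodynamic parameters shown to differ significantly between the study groups will be subjected to logistic regression analysis with stepwise addition mode";
- a univariate threshold of P "<0.1 on univariate analysis";
- a correlation filter: those passing, "except those being correlated with one another, will be included in multivariate logistic regression model".

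The stated purpose of the last model is "to identify independent predictors of MCA aneurysm", and on reporting the plan says "The results will be presented as odds ratios (ORs) and their 95% confidence intervals (CIs". Significance is p<0.05 throughout. Section 9 sets the size at "a minimum of 75 cases and 75 age- and sex-matched controls".

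The plan gives no cut-off for calling two variables correlated, no rule for which of a pair stays, and no stepwise entry threshold. It does not say whether the stepwise step and the P<0.1 screen form one chain or two models. Neither multiplicity control nor any allowance for selection appears, and the Limitations do not mention model selection.

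**The concern.** Two things go wrong, and they need different remedies. Testing many candidates at 0.05 each makes at least one chance finding likely, whether or not the model was fixed in advance. Separately, a nominal 95% CI has its stated coverage only if the model was not chosen by looking at the outcome. Here a parameter reaches the final model because its estimate in this sample was far enough from the null, so the final-model estimate tends to be too large and its interval is centred too far out.

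At stake is the main product of a study whose official title is about independent predictors: which parameters are named, how strong they appear, and how certain the reader may be. The named parameters also go on to the ROC analysis.

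**Working it through.** **Inputs from the document.** 15 candidates; at least 75 v 75; p<0.05 per test; univariate P<0.1. The plan states no power, effect size, SD or expected OR, so it has no figure of its own to reproduce. Cases per candidate: 75/15 = 5, counting near-duplicates such as r0 and p0 separately.

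**Assumptions, not in the document.** Vessel means, SDs and correlations; the correlation cut-off and tie-break; the stepwise entry threshold; effects in SD units; two-sided tests.

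**Step 1. Simple bound.** For k independent null tests, P(at least one p<α) = 1 − (1 − α)^k.

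- k = 15, α = 0.05: 1 − 0.95^15 = 53.7%
- k = 15, α = 0.1: 1 − 0.9^15 = 79.4%

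Correlation among the candidates and the later filters lower this, so the chain was simulated.

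**Step 2. Whole chain, no true association, 75 v 75.** Share of studies declaring at least one independent predictor:

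| Reading of the unspecified steps | Share |
|---|---|
| Both members of a correlated pair dropped | 22% |
| Cut at \|r\| ≥ 0.5, smaller p kept | 31% |
| Pearson p<0.05 filter, stepwise entry p<0.05, anatomy-like correlation | 34% |
| Same filters, independent candidates | 47% |
| No stepwise step; with or without the Mann-Whitney gate; \|r\| cut at 0.16, 0.3, 0.5 or 0.7 | 28-40% |

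Across all versions run, the range is about 21-47%.

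**Step 3. How much of this is selection?** Take seven parameters fixed in advance, no selection, null truth. Unadjusted p<0.05 gives 30.1% with any false claim, in line with 1 − 0.95^7 = 30.2%. Holm on the same model gives 4.0-4.4%. Fixing the model therefore barely changes the false-claim rate; the adjustment does.

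**Step 4. Effect of selection on ORs and CIs.** Among parameters retained in the final model:

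| True OR per SD | Mean log-OR ÷ true log-OR | Coverage of nominal 95% CI |
|---|---|---|
| 1.00 | not defined | 24% (20-72% across the readings without a stepwise step) |
| 1.11 | 3.6 | 64% |
| 1.22 | 2.2-2.3 | 86-89% |
| 1.35 | 1.6 | 93-95% |
| 1.65 | 1.2 | 96% |
| 2.23 | 1.14 | 93% |

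Example: at a true OR of 1.22 the mean reported OR is 1.59, and ln 1.59/ln 1.22 = 0.464/0.199 = 2.3. If stepwise entry at p<0.05 is the last gate, coverage for a null parameter is almost zero (0-0.2%), because entry itself nearly requires the interval to exclude 1.

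**Step 5. A mixed case.** With 3 true and 12 null independent candidates, the share of declared predictors that are false is 44%, 27%, 13% and 12% at true ORs of 1.22, 1.35, 1.65 and 2.23. Coverage over all declared predictors is 48%, 68%, 83% and 83%. At the two larger effects the shortfall comes mainly from the null survivors, since the true predictors' own intervals cover at 93-96%.

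**Step 6. Comparator without selection.** Five predictors fixed in advance, 75 v 75: coverage is 95.3% with no effect, 95.2% at a log-OR of 0.30 and 94.6% at 0.50. Mean log-ORs are 0.317 and 0.528, so ordinary small-sample bias is about 6% (0.317/0.30 = 1.06; 0.528/0.50 = 1.06). The excess in Step 4 is due to selection.

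**The case against.** Several counter-arguments have force.

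- A reader might infer that the false-claim rate is caused by model selection and would vanish with a fixed model. Step 3 shows otherwise. This stands, and it is why multiplicity and selection are separated here.
- A reader might infer that every reported OR is inflated and every interval too narrow. This is not supported. The document gives no expected effects, and for strong predictors the distortion is minor. Equally, strong effects cannot be presumed.
- The low coverage for null parameters is close to a tautology, since it conditions on having passed significance filters. That is fair as a comment on the figure, but the reader of the final model is in exactly that position.
- The plan does not say that only survivors will be reported. All listed variables are to be compared between groups, and the sentence on ORs is not confined to the final model. So one cannot claim that unselected parameters go unreported; the fault lies in how the final model's results are labelled and interpreted.
- No single figure is reliable, because the chain is not fully specified. That stands, and a range is given. None of the readings tried brings the false-claim rate near 5%.
- A short fixed model could remove listed primary outcomes. A model with p0, area ratio, asymmetry ratio, Φ1, Φ2, Vm and PI, for instance, would omit best-fit diameter, α and VFR, all listed in section 8. This stands and shapes the fix.
- The aim is to analyse relationships in an observational study, so an exploratory label might be enough. The plan, however, applies no such label.

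**Conclusion.** The concern holds in two distinct parts. Without multiplicity control, about 21-47% of studies run this way would name at least one independent predictor when none exists, and specifying the model in advance would not by itself cure that. Because selection uses the outcome, final-model ORs and CIs are unreliable for null or weak effects. The log-OR is overstated about 2-fold at a true OR of 1.22 per SD and about 1.6-fold at 1.35. Coverage is about 20-70% at OR 1.00-1.11 (lower still for a null parameter if stepwise entry at p<0.05 is the last gate) and about 90% at 1.22. Coverage is close to nominal from about OR 1.35, and inflation is small from about 1.65.

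The direction follows from the written procedure. The sizes rest on assumed vessel distributions, correlation cut-off and stepwise threshold. The document contains no results, so nothing here shows that any particular predictor is false.

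**What to change.** 1. Report the univariate OR and 95% CI for all 15 parameters, significant or not. Claim a predictor only on a Holm-adjusted p over the parameters tested. With 15, the smallest p must fall below 0.05/15 = 0.0033.
2. For the multivariable model, choose one of two routes and write it down:
   - **Fixed model.** Specify it without reference to the outcome, with one representative per redundant set: r or p of the same segment; Vm, p0 and VFR (VFR is Vm × p0 by definition); Φ1, Φ2 and α. Choose them so that every primary-outcome domain in section 8 is represented, and state which listed outcomes are then analysed only univariately.
   - **Selection kept.** Define every threshold and tie-break, bootstrap the entire chain with all filters redone in each resample, report inclusion frequencies and shrunken ORs, and label the survivors exploratory.

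Section 2 lists the study as completed in June 2017 and does not say whether groups have been compared. If they have, only the second route remains.

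Cost: revised analysis text and a few hours of analysis, with no new data. Fewer parameters will be declared and power per parameter falls, since Holm is conservative when candidates nearly duplicate one another.

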#### Limitations:

First, we will examine patients who had already been diagnosed with the MCA aneurysms. Thus, it cannot be excluded that at early stages of the aneurysm formation, morphometric and hemodynamic parameters of the MCA bifurcation might have been slightly different than they will be at the time of the study. Second, although the MCA aneurysms will be erased from the vascular images before the morphometric analysis, their presence might interfere with the bifurcation geometry. Third, the study might also suffer from a selection bias. Although the participants will be enrolled prospectively, some might be inadvertently excluded due to small size of aneurysms missed on CT scans.

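### ROC cut-offs are chosen in the same participants used to select the predictors, with no internal validation, so sensitivity and specificity reported at them will on average be too high; separately, no interval is planned for them

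*Combined protocol and SAP*

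**What the plan says.** The Analysis Plan (section 7) lists 15 candidate variables: six radii and cross-sectional areas, tortuosity, two ratios, three angles, mean velocity, volume flow rate and pulsatility index. They are screened by group tests, by univariate logistic regression at P<0.1 and by removal of mutually correlated variables. The survivors "will be included in multivariate logistic regression model, to identify independent predictors of MCA aneurysm". The predictors left at the end go to "receiver operating characteristic (ROC) analysis to identify their cut-off values with optimal sensitivity and specificity". The rule that defines the best cut-off is not named.

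On precision the plan says: "The results will be presented as odds ratios (ORs) and their 95% confidence intervals (CIs"). No interval is mentioned for a cut-off, a sensitivity, a specificity or an AUC.

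Section 9 describes one sample, "a minimum of 75 cases and 75 age- and sex-matched controls". The text available plans no split sample, cross-validation, bootstrap or external data set. The Limitations paragraph says that "the study might also suffer from a selection bias", but this refers to small aneurysms missed on CT, not to optimism from choosing predictors and cut-offs on the same data.

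**The concern.** A cut-off picked because it separates these particular cases and controls best is fitted partly to chance. Accuracy quoted at that cut-off in the same participants inherits the chance part, and new patients will not reproduce it. Screening the markers for significance first can add to this.

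The missing interval is a second, separate gap. It does not bias anything, but it leaves the reader unable to judge how uncertain the cut-off and its accuracy are. Published cut-offs are easily reused by others, so both gaps matter once the figures leave the paper.

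**Working it through.** **Inputs from the documents.** At least 75 cases and 75 controls (section 9); two groups (section 7); 15 candidates, significance level 0.05, ROC on the final predictors (Analysis Plan). There is no stated AUC, sensitivity, specificity or effect size, so there is no figure of the plan's own to reproduce.

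**Assumptions.** Normal markers with equal variance; group difference d of 0.3-1.0 SD; marker retained if Mann-Whitney p<0.05; criterion either Youden (maximum of sensitivity + specificity) or closest-to-corner.

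**Direction.** Let J = sensitivity + specificity - 1. For a marker with known direction, the best true value is J* = 2Φ(d/2) - 1. With Youden, the sample maximum is at least the sample value at the truly best cut-off, which averages J* without screening. The true J at any other cut-off is at most J*. So on average apparent J ≥ J* ≥ true J at the chosen cut-off. At d = 0.8, J* = 2Φ(0.4) - 1 = 2 × 0.655 - 1 = 0.31. It lies between the simulated apparent (0.367) and true (0.294) values below.

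**Size, 75 vs 75, one artery each** (20,000 retained samples per cell; repeat runs differ by at most 0.003). Excess = apparent J - true J at the chosen cut-off.

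| d (SD) | Youden | Closest-to-corner |
|---|---|---|
| 0.3 | 0.247 - 0.110 = 0.137 | 0.234 - 0.117 = 0.117 |
| 0.5 | 0.278 - 0.183 = 0.095 | 0.266 - 0.194 = 0.073 (before rounding) |
| 0.7 | 0.334 - 0.257 = 0.077 | 0.324 - 0.269 = 0.055 |
| 0.8 | 0.367 - 0.294 = 0.073 | 0.358 - 0.306 = 0.052 |
| 1.0 | 0.435 - 0.367 = 0.068 | 0.428 - 0.378 = 0.050 |

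Halving the sums at 0.7-1.0 SD gives about 2.5-4 points on each measure.

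**What selection adds.** For one pre-specified marker with AUC 0.70 and Youden, the excess is 0.074 without any screen. With 15 candidates, 3 of them real at AUC 0.70, it is 0.076 for the real markers that pass and 0.228 for null markers that pass. Per study 2.99 real and 0.59 null markers pass, so the average is (2.99 × 0.076 + 0.59 × 0.228) / 3.58 = 0.101. Adding the multivariable step, with an assumed rule that drops the weaker of any pair with |r| ≥ 0.5, does not shrink the excess: 0.070-0.081 / 0.051-0.060 at 0.7-1.0 SD, and 0.141-0.161 / 0.120-0.145 at 0.3 SD. So the cut-off choice drives the excess for moderate markers, and selection matters mainly for weak or null ones.

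**Other layouts, 0.7-1.0 SD.** With both control arteries (75 vs 150, within-person correlation 0-0.8) the excess is 0.057-0.067 / 0.041-0.046. With 150 vs 150 it is 0.045-0.050 / 0.033-0.034.

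**Would an ordinary binomial interval at the chosen cut-off suffice?** It leaves the point estimate as biased as before. Coverage of a nominal 95% interval at 0.5-1.0 SD depends on its type:

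| Interval | Youden | Closest-to-corner |
|---|---|---|
| Wald | about 85-90% | about 91-93% |
| Wilson | about 89-92% | about 92-94% |
| Clopper-Pearson | about 91-94% | about 94-95% |

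**What a bootstrap correction recovers** (patient bootstrap after the p<0.05 screen, J apparent / corrected / true, Youden). At 0.8 SD, 0.368 / 0.317 / 0.295: (0.368 - 0.317) / (0.368 - 0.295) = 0.051 / 0.073 = 70% of the excess. At 0.5 SD, 0.276 / 0.221 / 0.183: 0.055 / 0.093 = 59%. At 0.3 SD about 40% is removed. With closest-to-corner the shares are similar or somewhat lower. The correction does not undo selection.

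**The case against.** The best case against is about importance. At 0.7-1.0 SD the bias per measure is 2.5-4 points, below the sampling error of one proportion at n = 75: √(0.65 × 0.35 / 75) = 0.055. For stronger markers it falls further, to 0.057 / 0.043 in the sum at 1.5 SD and 0.049 / 0.038 at 2.0 SD. ROC is a secondary step: the second objective is "to analyse their relationship with aneurysm formation", and no outcome in section 8 is a cut-off. The plan promises cut-offs and only implies that sensitivity and specificity will be reported. All of this stands. It limits the weight of the point, not its direction. Averaging over more patients would reduce sampling error, whereas this error always leans the same way on average.

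It also stands that the magnitudes are assumed, and that the plan does not say which arteries enter the ROC analysis.

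A reader might infer several stronger things that are not supported:

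- *That the missing interval causes the bias.* It does not. The bias comes from choosing the cut-off on the data.
- *That every reported figure will be too high.* At 0.7-1.0 SD the sum is too high in 86-89% (Youden) or 76-77% (closest-to-corner) of samples, and both measures together in only 56-60% or 46-47%.
- *That any ordinary interval fails badly.* Marked under-coverage belongs to Wald with Youden. Clopper-Pearson with closest-to-corner is near nominal.
- *That AUC is inflated in the same way.* With full selection, apparent vs true AUC is 0.715-0.717 vs 0.714 at 0.8 SD. Only weak markers show a clear gap (0.631-0.647 vs 0.584 at 0.3 SD).

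**Conclusion.** The concern holds. Following the plan as written gives cut-off accuracy that is too high in expectation, and no interval accompanies it. The mean excess in sensitivity plus specificity is about 0.07-0.08 (Youden) or 0.05-0.055 (closest-to-corner) for markers differing by 0.7-1.0 SD, and larger for weaker ones. Confidence is high in the direction. The size rests on assumed normality, effect sizes, criterion and a 75 vs 75 layout, none of which can be checked in the documents except the minimum sample size.

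The main group comparisons are untouched, and nothing here suggests that they are invalid. This is a recommended improvement to a secondary analysis.

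**What to change.** Amend the Analysis Plan. Section 2 lists the study as completed, so if the ROC analysis has already been done, apply the same steps as a reanalysis.

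1. Name one cut-off criterion, such as Youden or closest-to-corner.
2. For each final predictor, bootstrap by patient, cases and controls separately. The Morphometric Analysis uses both sides of a person ("MCA bifurcations from the controls will be divided into two groups: R-MCA group with bifurcations of the right MCA", and likewise the left), so keep a patient's two arteries together. Resample matched sets if matching was individual, which section 9 does not say.
3. In each resample re-estimate the cut-off and apply it to the original data. Report optimism-corrected sensitivity and specificity with 95% intervals (bootstrap percentiles shifted by the estimated optimism), and a bootstrap 95% CI for the cut-off. State all as conditional on the predictor having been selected.
4. If AUC is reported, give a 95% CI with the same caveat, and do not call it optimism-corrected. The bootstrap left a single marker's AUC unchanged (0.650 before and after at 0.5 SD, true 0.638).
5. Label the cut-offs exploratory.

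Rerunning the selection steps in each resample, to show how often each predictor is reselected, is optional and needs the correlation rule to be written down first.

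The cost is a short paragraph and some programming, with no new patients or measurements. Reported accuracy becomes slightly less favourable. Cut-off intervals will be wide: on average 1.1-1.5 SD with Youden and about 0.7 SD with closest-to-corner. The correction is partial, about 70% of the excess at 0.7-1.0 SD and less for weaker markers, which is why the exploratory label is still needed.
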